6.1.2 Ipilimumab

There are no dose reductions for ipilimumab. For toxicity as outlined in this protocol, study therapy should be delayed until the AE improves to the stated level or should be discontinued permanently depending on severity (see table below). If a dose of ipilimumab is held for toxicity and cannot be resumed within 48 hours, the dose will not be made up, and the subject will continue to follow the standard dosing schedule. If the dose of ipilimumab is held for toxicity and can be resumed within 48 hours, the dose will be given, and the subject will continue to follow the standard dosing schedule (i.e., the next dose will be given on time).

6.1.3 Nivolumab

There are no dose reductions for nivolumab. For toxicity as outlined in this protocol, study therapy should be delayed until the AE improves to the stated level or should be discontinued permanently depending on severity (see table below). If a dose of nivolumab is held for toxicity and cannot be resumed within 48 hours, the dose will not be made up, and the subject will continue to follow the standard dosing schedule. If the dose of nivolumab is held for toxicity and can be resumed within 48 hours, the dose will be given, and the subject will continue to follow the standard dosing schedule (i.e., the next dose will be given on time).

Dose delay guidelines for nivolumab related adverse events

Recommendations for nivolumab modifications are below. When nivolumab is administered with ipilimumab, if nivolumab is held then ipilimumab should also be held.

Adverse Reaction	Severity*	Dose Modification
Colitis	Grade 2 diarrhea or colitis	Withhold dose ^a
	Grade 3 diarrhea or colitis	Withhold dose ^a when administered as a single agent
	Grade 4 diarrhea or colitis	Permanently discontinue when administered with ipilimumab
Pneumonitis	Grade 2 pneumonitis	Withhold dose ^a
	Grade 3 or 4 pneumonitis	Permanently discontinue
Hepatitis/non-HCC ^b	Aspartate aminotransferase (AST) or alanine aminotransferase (ALT) more than 3 and up to 5 times the upper limit of normal (ULN) or total bilirubin more than 1.5 and up to 3 times the ULN	Withhold dose ^a
	AST or ALT more than 5 times the ULN or total bilirubin more than 3 times the ULN	Permanently discontinue
Hepatitis/ HCC ^b	
 If AST/ALT is within normal limits at baseline and increases to more than 3 and up to 5 times the ULN If AST/ALT is more than 1 and up to 3 times ULN at baseline and increases to more than 5 and up to 10 times the ULN If AST/ALT is more than 3 and up to 5 times ULN at baseline and increases to more than 8 and up to 10 times the ULN 	Withhold dose ^c
	If AST or ALT increases to more than 10 times the ULN or total bilirubin increases to more than 3 times the ULN	Permanently discontinue
Hypophysitis	Grade 2 or 3 hypophysitis	Withhold dose ^a
	Grade 4 hypophysitis	Permanently discontinue
Adrenal Insufficiency	Grade 2 adrenal insufficiency	Withhold dose ^a
	Grade 3 or 4 adrenal insufficiency	Permanently discontinue

Adverse Reaction	Severity*	Dose Modification
Type 1 Diabetes Mellitus	Grade 3 hyperglycemia	Withhold dose ^a
	Grade 4 hyperglycemia	Permanently discontinue
Nephritis and Renal Dysfunction	Serum creatinine more than 1.5 and up to 6 times the ULN	Withhold dose ^a
	Serum creatinine more than 6 times the ULN	Permanently discontinue
Skin	Grade 3 rash or suspected Stevens-Johnson syndrome (SJS) or toxic epidermal necrolysis (TEN)	Withhold dose ^a
	Grade 4 rash or confirmed SJS or TEN	Permanently discontinue
Encephalitis	New-onset moderate or severe neurologic signs or symptoms	Withhold dose ^a
	Immune-mediated encephalitis	Permanently discontinue
Other	Other Grade 3 adverse reaction	
	First occurrence	Withhold dose ^a
	Recurrence of same Grade 3 adverse reactions	Permanently discontinue
	Life-threatening or Grade 4 adverse reaction	Permanently discontinue
	Grade 3 myocarditis	Permanently discontinue
	Requirement for 10 mg per day or greater prednisone or equivalent for more than 12 weeks	Permanently discontinue
	Persistent Grade 2 or 3 adverse reactions lasting 12 weeks or longer	Permanently discontinue

* Toxicity was graded per National Cancer Institute Common Terminology Criteria for Adverse Events. Version 4.0 (NCI CTCAE v4).

^a Resume treatment when adverse reaction improves to Grade 0 or 1.

^b HCC: hepatocellular carcinoma.

^c Resume treatment when AST/ALT returns to baseline.

Dose delay guidelines for ipilimumab related adverse events

Recommendations for nivolumab modifications are below. When nivolumab is administered with ipilimumab, if nivolumab is held then ipilimumab should also be held.

Mild to moderate adverse reactions	Action
Gastrointestinal: Moderate diarrhoea or colitis that either is not controlled with medical management or that persists (5-7 days) or recurs	1. Withhold dose until an adverse reaction resolves to Grade 1 or Grade 0 (or returns to baseline). 2. If resolution occurs, resume therapy. ^d 3. If resolution has not occurred, continue to withhold doses until resolution then resume treatment. ^d 4. Discontinue YERVOY if resolution to Grade 1 or Grade 0 or return to baseline does not occur.
Hepatic: Moderate elevations in transaminase (AST or ALT > 5 to ≤ 8 x ULN) or total bilirubin (> 3 to ≤ 5 x ULN) levels	
Skin: Moderate to severe (Grade 3) ^b skin rash or widespread/intense pruritus regardless of etiology	
Endocrine: Severe adverse reactions in the endocrine glands, such as hypophysitis and thyroiditis that are not adequately controlled with hormone replacement therapy or high-dose immunosuppressive therapy	
Neurological: Moderate (Grade 2) ^b unexplained motor neuropathy, muscle weakness, or sensory neuropathy (lasting more than 4 days)	
Other moderate adverse reactions^c	

^a No dose reduction of YERVOY is recommended.

^b Toxicity grades are in accordance with National Cancer Institute Common Terminology Criteria for Adverse Events Version 3.0 (NCI-CTCAE v3).

^c Any other organ system adverse reactions that are considered immune-related should be graded according to CTCAE.

^d Decision whether to withhold a dose should be based on severity.

^d Until administration of all 4 doses or 16 weeks from first dose, whichever occurs earlier.

ULN = upper limit of normal

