6.1 Dose Delays/Dose Modifications

All dose modifications should be based on the AE requiring the greatest modification and should be properly documented in source documents. Investigators may take a more conservative approach than the guidelines outlined below based on clinical judgment that is in the best interest of the subject. **NOTE:** if one or more study drugs are permanently discontinued, subjects may continue with the remaining drugs per protocol at the discretion of the treating physician if the subject is receiving clinical benefit.

For subjects with immune-related adverse events (irAEs), if the management guidelines suggest delay or discontinuation, both nivolumab and ipilimumab should be held or discontinued. In the event that ipilimumab must be permanently discontinued due to an AE which can be directly attributed to ipilimumab (e.g. an infusion reaction), nivolumab may be continued per protocol at the discretion of the treating physician.

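### Section 6.1.3 gives two rules on re-exposure after the same liver result: the nivolumab table discontinues permanently, the ipilimumab table withholds and resumes

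*Combined protocol and SAP*

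**What the plan says.** Section 6.1.3 has two dose-delay tables, one headed for nivolumab-related and one for ipilimumab-related adverse events.

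- **Nivolumab table, Hepatitis/non-HCC row** (the row for a renal cell population). The trigger "AST or ALT more than 5 times the ULN or total bilirubin more than 3 times the ULN" leads to permanent discontinuation. There is no upper bound and no exception for combined dosing. The step below it, AST/ALT above 3 and up to 5 times ULN or bilirubin above 1.5 and up to 3 times ULN, is a hold.
- **Ipilimumab table, hepatic row.** The trigger is "Moderate elevations in transaminase (AST or ALT > 5 to ≤ 8 x ULN", or total bilirubin above 3 and up to 5 times ULN. The action text withholds until recovery, then says "If resolution occurs, resume therapy". A footnote limits resumption: "Until administration of all 4 doses or 16 weeks from first dose, whichever occurs earlier".
- **Lead-in to the ipilimumab table.** It reads "Recommendations for nivolumab modifications are below", although the table is for ipilimumab.
- **Section 6.1.** For immune-related events, "if the management guidelines suggest delay or discontinuation, both nivolumab and ipilimumab should be held or discontinued".
- **Held doses.** Section 6.1.2: "If a dose of ipilimumab is held for toxicity and cannot be resumed within 48 hours, the dose will not be made up". Section 6.1.3 has the same rule: "If a dose of nivolumab is held for toxicity and cannot be resumed within 48 hours, the dose will not be made up".
- **Appendix 2, hepatic algorithm.** A footnote permits delay in place of discontinuation up to 8 times ULN for AST/ALT or 5 times ULN for bilirubin. The appendix describes itself as guidance, and its hepatic figure is not shown in the text available.

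**The concern.** A subject in Cycles 1–4 with, say, an ALT of 6 times ULN meets both hepatic triggers. One table ends antibody treatment for good; the other allows it to restart after recovery. If the two tables could be applied drug by drug there would be no clash, but Section 6.1 ties the antibodies together for immune-related events. Two sites could therefore treat the same laboratory result differently, one barring rechallenge and the other allowing it, each citing Section 6.1.3. What is at stake is re-exposure after liver toxicity in the few subjects affected.

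**Working it through.** The plan gives no figure on this point to reproduce. The check compares the ranges, looks for a rule that ranks the tables, and counts the doses that depend on the answer.

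**1. Overlap of the ranges (multiples of ULN)**

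| | AST/ALT | Bilirubin | Action |
|---|---|---|---|
| Nivolumab table | > 5, no upper bound | > 3, no upper bound | Permanently discontinue |
| Ipilimumab table | > 5 to ≤ 8 | > 3 to ≤ 5 | Withhold, resume on resolution |

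The second range lies wholly inside the first, so the two actions differ across all of it.

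One reading step is needed. The ipilimumab action text is printed beside the gastrointestinal row, and the action cells of the rows below, including the hepatic row, are blank. I read it as one merged cell, since those rows would otherwise have no action.

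**2. Is there a tie-break?**

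- Section 6.1 bases modification on whichever event needs the largest change. That ranks events, not two actions for one event.
- Section 6.1 lets investigators be stricter. That is optional.
- The Section 6.1 joint rule says hold or discontinue both, without saying which when the tables differ. Its one exception lets nivolumab continue when ipilimumab is stopped for an event directly attributable to ipilimumab. It has no reverse form.
- Appendix 2 leans toward delay, but is guidance only.

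The joint rule favours discontinuing both. Nothing states it.

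**3. Doses in Cycles 1–4 that depend on the answer**

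Inputs: Day 1 dosing in four 21-day cycles (Sections 5.4.2 and 5.4.3), so joint doses fall at weeks 0, 3, 6 and 9 and the period is 4 × 21 = 84 days = 12 weeks. Liver tests are scheduled on Day 1 of each cycle (Section 7). A held dose is not made up after 48 hours. Subjects started on steroids for an immune-related event must taper to 10 mg prednisone daily or less before resuming (Section 5.6.1).

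Let t be the week the event is found and R the weeks to recovery plus any taper, longer than 48 hours. The documents give no value for R, so a range is shown. Further doses = number of scheduled doses at week ≥ t + R.

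| Found at Day 1 of | t | R ≤ 3 | 3 < R ≤ 6 | R > 6 |
|---|---|---|---|---|
| Cycle 2 | 3 | 2 (weeks 6, 9) | 1 (week 9) | 0 |
| Cycle 3 | 6 | 1 (week 9) | 0 | 0 |
| Cycle 4 | 9 | 0 | 0 | 0 |
| Cycle 5 | 12 | 0 | 0 | 0 |

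The ceiling is 4 − k after dose k: 3, 2, 1, 0. It is reached only if no scheduled dose is missed, that is, an unscheduled test finds the event and recovery and taper finish before the next Day 1, or a held dose is resumed within 48 hours. The 16-week limit does not bind, since the last joint dose is scheduled at week 9.

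**4. Exposure after Cycle 4**

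The counts above leave out nivolumab maintenance: 480 mg every 28 days from Cycle 5 until progression or prohibitive toxicity (Sections 5.1.2 and 5.4.2). By reading:

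| Reading | Doses left in Cycles 1–4 | Nivolumab maintenance |
|---|---|---|
| Nivolumab table governs both | 0 | None |
| Ipilimumab table governs both | Step 3 counts, both antibodies | Available from Cycle 5 |
| Each table governs its own drug | Step 3 counts, ipilimumab only | None |

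The third reading sits badly with the Section 6.1 joint rule. Under the second, maintenance has no fixed number of doses and can be the larger difference, including for events found at Cycle 4 or 5.

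**The case against.** The best case for the plan is that the tables are not truly incompatible. Their headings separate them by drug. The ipilimumab table names the ipilimumab brand in its discontinuation step, and its resumption limit counts ipilimumab's four doses. Only the lead-in stretches it to nivolumab, and that looks like a copying slip. Section 6.1 then points to stopping both. Both tables are framed as recommendations, and stricter practice is allowed, so some variation between sites is intended.

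Much of this stands: the joint rule does lean toward discontinuation, and the merged-cell reading is an inference from a table extracted from PDF. What remains is that attributing hepatitis to one antibody during combined dosing is a judgement, the joint rule does not choose between hold and discontinue, and the lead-in as printed lets a site take the ipilimumab table as the nivolumab rule.

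Stronger readings a reader might infer are not supported:

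- *One table lets dosing continue through the event.* Both stop it at once.
- *DLT counts or the RP2D are affected.* Section 5.2.1 defines hepatic DLTs by its own limits (AST/ALT above 3 times ULN, bilirubin above 2 times ULN, not otherwise explained), without reference to these tables.
- *Appendix 2 is a third binding rule.* It is guidance, and its hepatic figure cannot be seen.
- *Up to 18 subjects are affected.* That is the lead-in maximum, not a count of subjects with such events.

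**Conclusion.** The inconsistency is real and minor. For AST/ALT above 5 and up to 8 times ULN, or bilirubin above 3 and up to 5 times ULN, Section 6.1.3 states two different rules on re-exposure, and no sentence says which governs. Section 6.1 favours discontinuing both antibodies but does not settle it.

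For an affected subject the difference is nil against at most 3 doses in Cycles 1–4 (2 or fewer when the event is found at a scheduled visit and the held dose is missed), plus maintenance if resumption covers nivolumab. This rests on the merged-cell reading and on the event being handled as immune-related. The documents give no event rate for this band. Accrual halts after the lead-in, and the conflict concerns only subjects still in Cycles 1–4, whose number is not given. No sample size, error rate, DLT definition or RP2D rule changes.

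**What to change.** 1. Amend the hepatic row of the ipilimumab table so that both antibodies are permanently discontinued above 5 times ULN for AST/ALT or 3 times ULN for bilirubin, in line with the Section 6.1 joint rule. Leave the lower hold as the nivolumab table has it; that table already holds ipilimumab when nivolumab is held.
2. Correct the ipilimumab table's lead-in so that it refers to ipilimumab.
3. State in Section 6.1 that Section 6.1.3 governs where Appendix 2 differs.

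The threshold is a clinical choice. If the clinical team prefers the 8 and 5 times ULN allowance, write that single rule into both tables.

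The cost is a protocol clarification and a site memo, with no added subjects, visits or tests. The downside of the stricter default is that some subjects in this band lose the option of rechallenge.

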6.2 Protocol Therapy Discontinuation

In addition to discontinuation from therapy related to toxicities as outlined in section 6.1, a subject will also be discontinued from protocol therapy and followed up per protocol under the circumstances outlined below. The reason for discontinuation of protocol therapy will be documented on the eCRF.

- Documented disease progression per RECIST 1.1.
- The treating physician thinks a change of therapy would be in the best interest of the subject
- The subject requests to discontinue protocol therapy, whether due to unacceptable toxicity or for other reasons
 - If a subject decides to prematurely discontinue protocol therapy (“refuses treatment”), the subject should be asked if he or she may still be contacted for further scheduled study assessments. The outcome of that discussion should be documented in both the medical records and in the eCRF.
- A female subject becomes pregnant

6.3 Protocol Discontinuation

If a subject decides to withdraw from the study (and not just from protocol therapy) all efforts should be made to complete the final study assessments. The site study team should contact the subject by telephone or through a clinic visit to determine the reason for the study withdrawal. If the reason for withdrawal is an adverse event, it will be recorded on the eCRF.

7. STUDY CALENDAR & EVALUATIONS

	Screen	Cycle= 21 days				Cycle= 28 days		Safety follow up ¹³	Long-term Follow up ¹⁴
	-28 days ¹	Cycle 1	Cycle 2	Cycle 3	Cycle 4	Cycle 5+		30/100 days (±7)	Q 6 months (±30)
		D1 ±3	D1 ±3	D1 ±3	D1 ±3	D1 ±3	D15 ±3 ¹²		
REQUIRED ASSESSMENTS									
Informed Consent	X								
Medical history; Diagnosis ¹	X								
Physical exam	X	X	X	X	X	X		D30	
Vital signs, ECOG Performance status ²	X	X	X	X	X	X		D30	
AEs & concomitant medications	X	X	X	X	X	X	X ¹²	X	
Drug compliance review (entinostat)			X	X	X	X	X ¹²	D30	
LABORATORY ASSESSMENTS									
Complete Blood Cell Count w/ diff (CBC)	X	X ¹¹	X	X	X	X	X ¹²	D30	
Comprehensive Metabolic Profile (CMP)	X	X ¹¹	X	X	X	X	X ¹²	D30	
Magnesium, Phosphate, Uric Acid, Lactate Dehydrogenase	X	X ¹¹	X	X	X	X	X ¹²	D30	
PT/INR and aPTT	X								
Thyroid Function (TSH, T4, free T3) ³	X		X		X	Q3cycles			
Pregnancy test WOCBP ⁴	X	X							
DISEASE ASSESSMENT									
CT of chest, abdomen and pelvis ⁵	X			X		X ⁵		D30 ⁵	Per SOC
Bone scan ⁵	X			X		X ⁵		D30 ⁵	Per SOC
MRI of brain ⁵	X								
TREATMENT EXPOSURE									
Entinostat		D1,8,15	D1,8,15	D1,8,15	D1,8,15	D1, 8, 15, 22			
Nivolumab		X	X	X	X	X	X ¹²		
Ipilimumab		X	X	X	X				
CORRELATIVE STUDIES									
Archival Tissue (required if available) ⁶	X								
Optional fresh biopsy ⁶	X		X						
Blood samples ⁷		X	X		X	Q2 cycle ⁷			

	Screen	Cycle= 21 days				Cycle= 28 days		Safety follow up ¹³	Long-term Follow up ¹⁴
	-28 days ¹	Cycle 1	Cycle 2	Cycle 3	Cycle 4	Cycle 5+		30/100 days (±7)	Q 6 months (±30)
		D1 ±3	D1 ±3	D1 ±3	D1 ±3	D1 ±3	D15 ±3 ¹²		
BANKING SAMPLES									
Whole Blood ⁸		X							
Unstained Slides (if available) ⁹		X							
Serum and Plasma ¹⁰		X						D30	
FOLLOW-UP									
Survival status, subsequent therapy									X

CBC with differential and platelet to include: WBC, ANC, Hgb, Hct, PLT. CMP to include sodium, potassium, chloride, creatinine, blood urea nitrogen; liver function tests (LFTs) to include AST, ALT, total bilirubin, alkaline phosphatase

Key to Footnotes

1: Medical History; other data to be obtained during this assessment includes: diagnosis and staging to include pathology report and staging documentation. a smoking history questionnaire and trial awareness question. In addition, prior anti-cancer treatment should be documented.

2: Vital signs to include blood pressure, weight, and height (screening only) and ECOG performance status.

3: Thyroid function to be checked at screening, Cycle 2 Day 1, Cycle 4 Day 1, then every 3rd cycle thereafter starting with Cycle 6. More frequent testing is at the discretion of the site investigator. TSH will be obtained. T4 and T3 including free versus total testing is at the discretion of the site investigator.

4: For women of childbearing potential (WOCBP): serum pregnancy test during screening and a urine pregnancy test within 3 days prior to first dose of study drugs. If the screening serum test was done within 3 days prior to receiving the first dose of study drugs, a urine test is not required.

5: Tumor response assessment will be performed at screening, prior to Cycle 3 Day 1 then prior to Cycle 5 (±7); Tumor imaging to be performed every 8-12 weeks after Cycle 5 based on investigator discretion. Tumor imaging to be done at treatment discontinuation at discretion of investigator. Baseline bone scan will be obtained if there is any suspicion of metastatic bone involvement. If bone scan is positive at baseline, it will be included with subsequent tumor response assessments as noted above at the discretion of the treating physician. MRI of brain should be performed at screening only to evaluate for the presence of brain metastases. Additional imaging of the brain will be at the discretion of the treating physician. Tumor imaging modality used should be consistent throughout trial.

6: Archival tissue from a metastatic lesion or nephrectomy (metastatic lesion preferred) is required if available and will be obtained at screening. If archival tissue is unavailable, patients will be given the option to consent to a biopsy during the screening phase prior to Cycle 1 Day 1 treatment. All subjects with accessible tumor will be given the option to consent to a second optional biopsy on Cycle 2 Day 1. The Cycle 2 Day 1 samples will be collected ~2 hours following the most recent dose of entinostat. To ensure that these samples are obtained at the correct time, patients are urged to take their entinostat dose in the clinic on the day of on-treatment sample collection. The time of the entinostat dose and the time of sample collection must be recorded.

7: Serial blood samples for PBMCs and plasma, serum will be collected prior to treatment Cycle 1 Day 1, Cycle 2 Day 1, Cycle 4 Day 1, and then every 2nd cycle thereafter starting with Cycle 6.

8: Whole blood for banking is to be collected at Pre-Treatment Cycle 1 Day 1. See CLM for collection, processing, labeling and shipping instructions.

9: Submission of unstained slides for banking from an archived FFPE tumor block (if available). See CLM for collection, labeling, and shipping instructions.

10: Serum and plasma for banking are to be collected at Pre-Treatment Cycle 1 Day 1 and at the 30-Day Safety Follow up visit. See CLM for collection, labeling, processing, and shipping instructions.

11: If screening (baseline) CBC and CMP (including Mg, Phos, uric acid and LDH) were performed within 7 days of Day 1 of treatment, these do not need to be repeated. All laboratory assessments should be done prior to treatment.

12: During maintenance, subjects will receive nivolumab IV over 30 minutes at 480 mg on Day 1 of each cycle. Subjects that do not tolerate every 4 week dosing regimen may receive nivolumab 240 mg IV over 30 minutes on Day 1 and Day 15 of each cycle. Those subjects receiving nivolumab on Day 15 will have laboratory testing as well as AE and conmed assessment. These subjects will continue every 2 week dosing for the remainder of study treatment.

13: A safety follow-up visit will occur 30 days (\pm 7 days) after the last dose of treatment. AEs will be collected for 100 days after the end of treatment. This may be accomplished via phone call, email or medical records.

14: Subjects who discontinue treatment for any reason will be followed every 6 months until death, withdrawal of consent, or the end of the study, whichever occurs first. Follow up may be accomplished via clinic visit, phone call, or other avenues as appropriate.

